6.3 Exclusion Criteria

1. Previous documented COVID-19 infection.
2. Use of investigational agents for prophylaxis against COVID-19 within 90 days of the start of the study, including Evusheld monoclonal antibodies.
3. Ongoing therapy for acute cellular or antibody mediated rejection.
4. Intravenous immunoglobulins (IVIG) administration within the prior 3 months or ongoing IVIG therapy.
5. Anaphylaxis or allergic reaction to any prior vaccines.
6. History of anaphylaxis or other significant adverse reaction requiring medical intervention after receipt of a vaccine.
7. Is acutely ill or febrile 24 hours prior to or at the Day 1 visit. Fever is defined as a body temperature $\geq 38.0^{\circ}\text{C}/100.4^{\circ}\text{F}$. Participants meeting this criterion may be rescheduled within the

relevant window periods. Afebrile participants with minor illnesses can be enrolled at the discretion of the investigator.

8. Pregnant or breastfeeding.
9. Has a medical, psychiatric, or occupational condition that may pose additional risk as a result of participation, or that could interfere with safety assessments or interpretation of results according to the investigator's judgment.
10. Known history of hypertension (HTN) with systolic blood pressure (BP) > 180 mm Hg at the Day 1 visit.
11. Known history of hypotension with systolic blood pressure < 85 mm Hg at the Day 1 visit.
12. Bleeding disorder considered a contraindication to IM injection or phlebotomy.
13. Active malignancy diagnosed within previous 4 years (excluding non-melanoma skin cancer).
14. Received a major surgery including lung transplantation in the past 3 months.

Exclusion of Specific Populations:

Because the effects on the fetus are not known, pregnant women will not be eligible for the trial. Women of childbearing potential (<1 year since start of menopause) must utilize a highly effective method of contraception and will be required to have a negative urine or serum pregnancy test within 24 hours prior to the vaccination. Children will not be included in this trial as presently there are no children receiving lung transplantation at UCLA. Should the outcome of this trial be deemed acceptable, additional trials may be initiated, including those in other populations.

7 CONCURRENT MEDICATIONS

This trial design allows for participants in all study arms to receive other investigational drugs for COVID-19 after Day 45 of the study.

7.1 Allowed Medications and Treatments

Standard therapy for COVID-19 is allowed except for treatments noted in the exclusion criteria described above and as noted in the prohibited medications section below. Based on inclusion criteria, participants will be required to be on a regimen of triple immunosuppression including prednisone, mycophenolate mofetil (minimum 250 mg bid) or mycophenolate sodium (minimum 180 mg bid), and tacrolimus at the Day 1 study visit. Participants receiving IVIG or augmented immunosuppression for treatment of acute rejection or antibody mediated rejection will be excluded from the study.

7.2 Prohibited Medications and Treatments

Use of investigational agents for prophylaxis against COVID-19 within 90 days of the start of the study, including Evusheld monoclonal antibodies. Use of investigational agents for prophylaxis including Evusheld against COVID-19 for at least 30 days after study vaccination, since this will affect the antibody-based secondary endpoints.

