5.3 Safety Evaluations

The study will use a Data and Safety Monitoring Board (DSMB). DSMB reviews are required for study halting and restarting. Reporting to regulatory bodies (IRB, FDA) will only be required for serious adverse events judged by the treating physician and study investigators to be potentially related to the administration of the study drug, including suspected, unexpected, serious adverse reactions (SUSAR, Section 11). All other adverse events will be reviewed by the study investigators and reported per FDA and IRB regulations. The study will be overseen by CTSI Data and Safety monitoring Board. By allowing CTSI DSMB to oversee the study, the PI agrees to abide by the CTSI DSMB's policies and procedures as outlined in the DSMB charter.

Safety evaluations:

1. **Visit 1:** Day 1 (booster day): informed consent, med history, inclusion criteria review, physical exam, blood draw, administration of booster, 30-minute observation.
2. **Telephone visit Day 3:** Review for AEs, SAEs, AESIs and MAAEs.
3. **Visit 2:** Day 7 - blood draw, physical exam and review for AEs, SAEs, AESIs and MAAEs.
4. **Visit 3:** Day 30 - blood draw, physical exam and review for AEs, SAEs, AESIs and MAAEs.
5. **Telephone visit Day 90:** Review for AEs, SAEs, AESIs and MAAEs.
6. **Telephone visit Day 180:** Review for AEs, SAEs, AESIs and MAAEs.

The following labs will be collected at baseline and clinic follow-up visits.

1. Serum collected for antibody levels.
2. PBMCs collected for cellular response assays including flow cytometry with intracellular staining.
3. Whole blood collected for cellular response assays.
4. Troponin, CK and cytokines banked from Day 0, 7 and 30.

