6.2 Inclusion Criteria

1. All adult lung transplant recipients (age ≥ 18 at the time of consent) who received all of their COVID-19 vaccines after lung transplantation.
2. Received three or four doses of either the Moderna mRNA-1273 or Pfizer BNT162b2 vaccine with the last dose received at least 4 months prior to study enrollment.
3. Currently receiving standard regimen of three drug immunosuppression with prednisone, tacrolimus and mycophenolate mofetil (minimum 250 mg bid) or mycophenolate sodium (minimum 180 mg bid).

4. Agrees not to receive other investigational agents for prophylaxis against COVID-19 including Evusheld monoclonal antibodies for at least 30 days after the study vaccine.
5. Understands and agrees to comply with the study procedures and provides written informed consent.
6. Is in stable health without any new or worsening medical conditions in the opinion of the Investigator.
7. Female participants of childbearing potential (<1 year since start of menopause) may be enrolled in the study if the participant fulfills all the following criteria:
 - a. Has a negative pregnancy test at Visit 1 Day 1.
 - b. Has practiced adequate contraception or has abstained from all activities that could result in pregnancy for at least 28 days prior to the first injection (Day 1).
 - c. Has agreed to continue adequate contraception or practice abstinence through 3 months following the booster injection (Day 90).
 - d. Is not currently breastfeeding.
 - e. Adequate female contraception is defined as consistent and correct use of a Food and Drug Administration (FDA) approved contraceptive method in accordance with the product label. For example:
 - i. Barrier method (such as condoms, diaphragm, or cervical cap) used in conjunction with spermicide
 - ii. Intrauterine device
 - iii. Prescription hormonal contraceptive taken or administered via oral (pill), transdermal (patch), subdermal, or IM route
 - iv. Sterilization of a female participant's monogamous male partner prior to entry into the study
 - v. Note: periodic abstinence (e.g., calendar, ovulation methods) and withdrawal are not acceptable methods of contraception.

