9.1.6 Adverse Events

Information regarding occurrence of adverse events will be captured throughout the study. Duration (start and stop dates and times), severity/grade, outcome, treatment and relation to study drug will be recorded on the case report form (CRF).

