10.2 Visit 1 Day 1 (Clinic): Booster Vaccine Day

1. For participants who meet inclusion/exclusion criteria, the investigator team will again review the study with the participant (or participant's legal representative) in person and obtain written informed consent and HIPAA authorization.
2. Record demographic data.
3. Record medical history.
4. Review of birth control history with female participants of childbearing potential (<1 year since start of menopause).

5. For women of childbearing potential, counsel participants to use adequate birth control methods required during the trial to avoid pregnancy.
6. For women of childbearing potential, urine pregnancy test will be checked prior to study drug administration on Visit 1 (Day 1).
7. Confirmation participants meet all inclusion criteria and no exclusion criteria review.
8. Review pre-study concomitant medications and therapies and record on the appropriate CRF.
9. Review of influenza and any all 2019-CoV vaccinations or other experimental coronavirus vaccines.
10. Vital signs (HR, BP, temperature, oximetry), and height and weight for determination of BMI.
11. Full physical exam will include assessments of the following organs and organ systems: skin, head, ears, eyes, nose, and throat (HEENT), neck, lungs, heart, liver, spleen, abdomen, extremities, lymph nodes (axillary and cervical), and nervous system.
12. Obtain blood samples for baseline: Total immunoglobulins (IgG, IgA, IgM), anti-RBD, anti-spike binding and neutralizing antibody levels, PBMCs collected for cellular response assays including flow cytometry with intracellular staining, whole blood collected for cellular response assays, troponin / CK and cytokines for storage.
13. Confirm group assignment: standard-dose, mid-dose or high-dose group.
14. Inform participants of their designated dose.
15. Administration of booster vaccine.
16. Participants will be observed for 30-minutes post injection administration.
17. Dispense daily diary of symptoms for first 7 days after injection dispensed to participant measuring FDA Toxicity Grading Scale and adverse events.

10.3 Visit 2 Day 3 +/-1 Day (Phone – 2 days post booster):

1. All participants will complete a daily diary of solicited and unsolicited AEs from the vaccination until 7 days post-vaccination. Reactogenicity will be measured by the occurrence of solicited injection site and systemic reactions for the first 7 days post-vaccination utilizing the FDA Toxicity Grading Scale.

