2. Participants will be contacted by telephone to query for safety events and review daily diaries. Based on the information collected, participants may be asked to return to the clinic for evaluation for an unscheduled visit.
3. Review daily diaries, AEs (solicited and unsolicited), SAEs, AESIs and MAAEs.
4. Participants will contact their primary care doctor, lung transplant pulmonologist or study principal investigator with any SAEs, AESIs or MAAEs.

10.4 Visit 3 Day 7 +/-2 Days (Clinic Visit – 6 days post booster):

1. Vital signs (HR, BP, temperature, oximetry), and height and weight for determination of BMI.
2. Symptom-directed (targeted) physical exam. Targeted physical examinations should also include an assessment for signs suggestive of AEs and AESIs. Interim or unscheduled physical examinations will be performed at the discretion of the PI or appropriate sub-investigator, if necessary, to evaluate AEs or abnormal clinical laboratory test results.
3. Obtain blood samples for follow-up: Total immunoglobulins (IgG, IgA, IgM), anti-RBD, anti-spike binding and neutralizing antibody levels, PBMCs collected for cellular response assays including flow cytometry with intracellular staining, whole blood collected for cellular response assays, troponin / CK and cytokines for storage.

5. Review daily diaries, AEs (solicited and unsolicited), SAEs, AESIs and MAAEs.

10.5 Visit 4 Day 30 +/- 7 Days (Clinic – 29 days post booster):

1. Vital signs (HR, BP, temperature, oximetry), and height and weight for determination of BMI.
2. Symptom-directed (targeted) physical exam. Targeted physical examinations should also include an assessment for signs suggestive of AEs and AESIs. Interim or unscheduled physical examinations will be performed at the discretion of the PI or appropriate sub-investigator, if necessary, to evaluate AEs or abnormal clinical laboratory test results.
3. Obtain blood samples for follow-up: Total immunoglobulins (IgG, IgA, IgM), anti-RBD, anti-spike binding and neutralizing antibody levels, PBMCs collected for cellular response assays including flow cytometry with intracellular staining, whole blood collected for cellular response assays, troponin / CK and cytokines for storage.
4. Review daily diaries, AEs (solicited and unsolicited), SAEs, AESIs and MAAEs.

10.6 Visit 5 Day 90 +/- 7 Days (Phone – 89 days post booster):

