APPENDIX 1. SCHEDULE OF EVENTS

	Screening Day -30 to Day 0	Visit 1 Day 1 Clinic	Visit 2 Day 3 Phone +/-1 day	Visit 3 Day 7 Clinic +/-2 days	Visit 4 Day 30 Clinic +/-7 days	Visit 5 Day 90 Phone +/-7 days	Visit 6 Day 180 Phone +/-7 days	Unscheduled visit as needed
Informed Consent		X						
Demographic data		X						
Medical History		X						
Eligibility review	X	X						
Con meds		X						
Pre-study meds		X						
Review CoV vaccinations		X						
Height		X						
Weight		X		X	X			
Vital Signs (HR, BP, temperature, oximetry)		X		X	X			
Full physical exam		X						X

Phase I/II, Open-label Dose-finding Trial of High-Dose mRNA-1273 Booster for Lung Transplant Recipients
Confidential

Targeted physical exam				X	X			
Blood draw*		X		X	X			X
Group assignment		X						
IP administration		X						
30-minute post-dose observation		X						
Review AEs, SAEs, AESIs, MAAEs			X	X	X	X	X	X
Review myocarditis and pericarditis symptoms			X	X	X	X	X	X
Dispense daily diary		X						
Diary review			X	X				
Pregnancy test (women of child-bearing potential)		X						
Birth control history (women of child-bearing potential)		X						
Review participants' use of appropriate birth control (if applicable)		X						

*Baseline labs must be drawn before vaccine dose. Day 7 must be drawn +/- 2 days. All other labs can be drawn +/- 7 days.

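### The 30-day bar on Evusheld-type prophylaxis can lapse before the Day 30 antibody sample is drawn; Section 7 gives a conflicting date, and no medication question follows Day 1

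*Combined protocol and SAP*

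**What the plan says.** Section 7.2 prohibits investigational prophylactic agents, Evusheld among them, "for at least 30 days after study vaccination, since this will affect the antibody-based secondary endpoints". Inclusion criterion 4 (Section 6.2 and the synopsis) has the participant agree to the same limit, "including Evusheld monoclonal antibodies for at least 30 days after the study vaccine".

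The opening of Section 7 gives a different date. It lets participants in every arm "receive other investigational drugs for COVID-19 after Day 45 of the study".

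Section 10.5 sets the antibody visit as "Visit 4 Day 30 +/- 7 Days" and equates Day 30 with 29 days after the booster. The Appendix 1 footnote allows the same window for the sample: "All other labs can be drawn +/- 7 days".

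Medication is reviewed once, at Visit 1: "Review pre-study concomitant medications and therapies and record on the appropriate CRF" (Section 10.2). Appendix 1 marks its two medication rows at Visit 1 only, and Sections 10.3 to 10.8 list no later review.

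Section 14.1 assigns the secondary endpoints to the PP set. That set requires adherence to the protocol and that the participant can be evaluated for the endpoint concerned. It names an exclusion for anti-N antibody at baseline, but none for a sample drawn after an antibody product.

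**The concern.** The bar exists to keep the Day 30 antibody sample free of product-derived antibody; Section 7.2 gives that as its reason. A bar with that purpose should last until the sample is taken. Under the 30-day rule it can end up to 6 days earlier.

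If a participant received such an agent in those days and was then sampled, the measured IgG level or neutralising titre would be counted as response to the booster. In the standard-dose arm this would hide part of a dose effect; in the high-dose arm it would inflate it. The trial is open-label and participants are told their dose, so equal uptake across arms cannot be taken for granted. With at most 18 per group in the PP set, a single value carries weight. The primary safety analysis does not depend on these values.

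**Working it through.** **Dates.** Study day = 1 + days since vaccination (vaccination on Day 1, Section 8.4.3).

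- Check against the plan: Day 30 − Day 1 = 29 days, as Section 10.5 states.
- Last day of the 30-day bar: 1 + 30 = Day 31.
- Draw window: 30 − 7 = Day 23 to 30 + 7 = Day 37, which is 15 permitted days.
- Uncovered days: Day 32 to Day 37, which is 6 of the 15. This counts days, not the share of participants drawn late.
- Section 7 date: 45 − 37 = 8 days beyond the last permitted draw, and 45 − 31 = 14 days beyond the 30-day bar.

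**The two rules side by side.** If Section 7 covers prophylaxis, the draw is protected, but the section disagrees with 7.2 and inclusion 4. If it does not, Days 32 to 37 are open. The text does not say which applies.

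**Scale of one exposed value (illustration only).** Inputs from Section 14.6: mean log10 IgG increases 0.23 and 0.91, SD 0.63, two-sided 0.05. Group size from Section 14.1 and Table 1: 18 per arm in a full PP set.

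- Plan's own figure: difference 0.91 − 0.23 = 0.68. The t-test needs 14.5, so 15 per group for 80% power, as stated.
- Power with 18 per group and nobody exposed: 88.2% (noncentral t).
- Detectable percentage: one participant moves it by at most 1/18 = 5.6 points, and only if otherwise below the LLOQ.

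The documents give no effect of these products on IgG, so the shifts below are assumptions. For one exposed standard-dose participant, the expected difference is 0.68 − shift/18. Power comes from 200,000 simulated trials with a pooled t-test, the SD being estimated from data that include the exposed value. For one exposed high-dose participant, the expected difference is 0.68 + shift/18.

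| Assumed shift (log10) | Difference, standard-dose participant exposed | Power | Difference, high-dose participant exposed |
|---|---|---|---|
| 0.5 | 0.65 | 85.2% | 0.71 |
| 1 | 0.62 | 80.5% | 0.74 |
| 2 | 0.57 | 65.9% | 0.79 |

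Leaving that one participant out instead (17 versus 18) gives 87.2%.

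**The case against.** The strongest reply is that the protocol already covers the draw. Inclusion 4 classes Evusheld among investigational agents, Section 7 speaks of investigational COVID-19 drugs generally, and a 30-day minimum is also met by waiting until after Day 45. Read together, the clauses leave 8 days to spare. This is a fair reading, and it rules out calling the gap certain. It does not settle the matter, because the 30 days are what the participant agrees to and what the prohibited list states, so staff could reasonably apply them.

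A reader might also infer that an exposed participant must stay in the PP set. The documents do not support that. The requirement that participants can be evaluated for the endpoint could be used to remove the sample, and if Section 7 applies, use would be non-adherence. But that requirement is undefined, so removal is left to judgement.

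Detection is partial rather than absent. Treatment given for an adverse event is recorded (9.1.6), medically attended events include unscheduled visits for any reason (11.1), and use of a prohibited medication calls for a violation form (13). None of these prompts a question about elective prophylaxis given at a routine visit.

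Finally, harm needs a draw after Day 31 and use of an agent in the few days before it. The documents give no rate for either. That stands in full.

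**Conclusion.** The dates do not fit together. Under the 30-day rule the bar runs through Day 31 and the sample may be drawn to Day 37. Section 7's Day 45 would close the gap if it governs prophylaxis, but the protocol does not say so. Under the 30-day reading, use on Days 32 to 37 before a late draw is not clearly a violation, may stay in the PP set and may go unrecorded.

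The documented size is 6 days. A reader might take the power figures as an expected loss, or conclude that the Day 30 results will be contaminated. Neither follows: the shifts are assumed, and the frequency of late draws and of use is unknown. What the illustration does show is that, under those shifts, omitting one exposed standard-dose value costs about 1 point of power, while keeping it costs from 3 points (88.2 − 85.2) to 22 (88.2 − 65.9). The consequence is confined to the secondary antibody endpoints.

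**What to change.** 1. **Bar.** In the synopsis, inclusion 4 and Section 7.2, state that these agents are barred for at least 30 days after vaccination and until the Day 30 sample has been drawn, Day 37 at the latest. Keep the 30-day minimum. A bar that ended at the draw alone could end on Day 23, inside the unsolicited adverse event period (to Day 30) and the 28-day halting windows. Make Section 7 consistent, or simply apply Day 45 to prophylaxis. If prophylaxis is clinically needed sooner, give it and record it, drawing the sample first if the visit window is open.
2. **Detection.** Add one dated question on anti-SARS-CoV-2 antibody products and IVIG at the Day 3, 7 and 30 visits (Sections 10.3 to 10.5 and Appendix 1).
3. **Analysis.** In Section 14.1, exclude antibody results drawn after such a product from the PP antibody analysis in every arm, and report the counts by dose group.

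**Cost.** An amendment with IRB approval, one CRF field and 60 × 3 = 180 short questions. Some participants may wait up to 37 − 31 = 6 more days for prophylaxis, or up to about 45 − 31 = 14 if Day 45 is applied. A few antibody values may be lost; one lost value lowers planned power from about 88% to 87%.

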8 STUDY TREATMENTS

8.1 Method of Assigning Participants to Treatment Groups

This is a Phase I/II open-label dose-finding trial among lung transplant recipients who received three or four mRNA vaccine doses (mRNA-1273 or BNT162b2) after lung transplantation to: standard-dose (50 ug), mid-dose (100 ug) or high-dose (200 ug) mRNA-1273 booster vaccine. Participants will be enrolled into three dose groups: 1) Standard-dose – 20 participants, 2) Mid-dose – 20 participants, 3) High-dose – 20 participants. The first 2 participants in both the mid-dose and high dose groups will be considered the ‘sentinel’ group. Participants in the sentinel group will receive the vaccine and undergo a 7-day observation period for safety and reactogenicity before additional participants are enrolled into that dose group.

Overall study enrollment will begin with the mid-dose sentinel group (n=2). During the observation period for the mid-dose sentinel group, we will enroll two participants into the standard-dose group. Once the mid-dose sentinel group completes their 7-day observation period without triggering halting rules and is approved to proceed by the DSMB, we will enroll the next 27 participants (Cohort 1) with a 2:1 randomization into the mid-dose (n=18) and standard-dose (n=9) groups.

Once all 20 participants have received their mid-dose vaccine without triggering halting rules and is approved to proceed by the DSMB, we will enroll the high-dose sentinel group (n=2). Once the high-dose sentinel group completes their 7-day observation period without triggering halting rules and is approved to proceed by the DSMB, we will enroll the next 27 participants (Cohort 2) with a 2:1 randomization into the high-dose (n=18) and standard-dose (n=9) groups. All 20 participants in the mid-dose group will be enrolled prior to enrollment of the high-dose group.

We will perform stratified randomization for the two cohorts based on: 1) the number of prior doses, and 2) prior receipt of any BNT162b2 vaccines. Randomization will be done by the UCLA Clinical and Translational Science Institute (CTSI) statistics team based on scheduled participants prior to the study visit. The 6 participants in the sentinel (n=4) and initial (n=2) groups (Table 1) will be assigned into the 3 groups based on their scheduled visit day.

If the halting criteria is triggered for the high-dose group and further enrollment of this group is not recommended by the study investigators, DSMB or IRB, the study will continue randomized enrollment into the mid-dose and standard-dose groups with a 1:2 ratio to complete the enrollment of 60 participants total. Since the expected immunogenicity difference between the mid-dose and standard-dose group is smaller, we will require more participants to detect a difference between these two groups. The 1:2 enrollment ratio into the mid-dose and standard-dose groups will even the distribution of participants into these two groups. The primary endpoint analysis for safety and reactogenicity will not be affected by a restriction of participants into the mid-dose and standard-dose groups.

